5.2. General Considerations

Unless otherwise noted, continuous data will be summarized with the following descriptive statistics: number of observations (n), mean, standard deviation (STD), minimum, median, and maximum. Categorical data will be summarized with frequencies (n) and percentages (%). In cases where missing data cause percentages not to sum to 100, a missing data row will be provided. Percentages will use column totals as the denominator unless otherwise indicated. For time to event variables, the Kaplan-Meir curves will be presented if the number of patients is more than 5.

All data in the database will be used in the analysis, with the exception of exclusions defined in section 5.7 for efficacy analyses. All study data will be included in study data listings. Missing data will generally not be imputed, unless otherwise stated.

All summaries will be presented by dose cohort, and may also be presented for LTB and HTB patients separately as specified. All summaries will be descriptive. No formal hypothesis testing is planned.

5.3. Disposition of Patients

The number and percentage of patients receiving study treatment who completed the treatment period and study period along with the associated reasons for discontinuation from treatment and/or withdrawal from study will be presented by dose cohort.

5.4. Demographic, Baseline Characteristics, and Disease History

The following baseline and demographic characteristics will be summarized by descriptive statistics by dose cohort for ITT population:

- Race, ethnicity, age, sex, height, weight
- Prior MDS Therapies, time from diagnosis; Prior erythropoiesis stimulating agents (ESA); IPSS and IPSS-R risk group; WHO Subtypes
- Baseline ECOG performance status
- Baseline transfusion status (LTB or HTB)
- Baseline hemoglobin for LTB patients only and baseline transfusion burden for HTB patients only.
- Baseline transfusion burden for patients with 2 units or more baseline transfusion.
- Baseline erythropoietin (EPO) and baseline serum ferritin
- RS status and SF3B1 mutation status; any splicing factor (yes or no)
- Baseline bone marrow blasts
- Baseline iron chelation therapy

Demographic and baseline data, medical history, and disease history data will also be listed for each patient.

5.5. Study Drug Exposure

Study drug exposure will be descriptively summarized by dose cohort for safety population and will present the duration of exposure, the number of treatment cycles, the total dose administered, the number of patients with dose delay and reduction, and the number of patients with dose increase (for expansion cohorts only).

The duration of exposure will be calculated as (last dose date – first dose date) + 21.

The total number of cycles will be summarized by presenting the number and percentage of patients in each category.

The total dose administered is the total amount of doses a patient received during the treatment period.

The number of patients experiencing dose delay and reduction will be summarized by dose cohort. For the expansion cohort, the number of patients with dose increase will also be summarized.

Study drug administration details will be listed for each patient.

5.6. Prior and Concomitant Medication and Procedures

5.6.1. Prior and Concomitant Medication

The prior and concomitant medications are coded with WHO dictionary. The medications will be presented for the safety population.

Medications will be assigned as prior or concomitant based on the following rules:

- If both the start and stop date exist and are before the first dose date of study drug, the medication will be counted as prior.
- If the start date is on or after the first dose date of study drug, the medication will be counted as concomitant.
- If the start date is before the first dose date of study drug and the stop date is after the first dose date of study drug or the medication is ongoing, the medication will be counted as prior and concomitant.
- If the start date is missing and the stop date is before the first dose of study drug, the medication will be counted as prior.
- If the start date is missing and the stop date is after the first dose of study drug or the medication is ongoing, the medication will be counted as concomitant.
- If the start and stop dates are missing, the medication will be counted as concomitant.

All prior and concomitant medications will be listed for each patient.

5.6.2. RBC Transfusions

The complete RBC transfusion records prior to and during treatment will be listed for each patient. The hemoglobin values prior to transfusion will also be listed.

5.6.3. Non-Medication Procedures

Non-medication procedures will be coded using MedDRA Version 20.0 or higher. All non-medication procedures will be listed for each patient.

5.7. Efficacy Analyses

The analyses for all efficacy endpoints will be performed using the ITT population.

All efficacy summaries will be presented by dose cohort for LTB and HTB patients separately. No formal hypothesis testing is planned. In addition, summaries will also be provided for the following group of patients:

- All patients in the ITT population
- Lower dose group includes patients on 0.125, 0.25 and 0.5 mg/kg dose cohorts
- Higher dose group includes patients on 0.75 mg/kg and above

- Patients in the expansion cohorts 1, 2A, 2B, and 3
- Patients in 0.125 to 0.50 mg/kg dose cohorts, and
- Patients in 0.75 to 1.75 mg/kg dose cohorts.

Efficacy Results will also be summarized with the following groups:

- All RS+ patients
- All RS- patients
- RS+ patients in the high dose (≥ 0.75 mg/kg) cohorts, and
- RS- patients in the high dose (≥ 0.75 mg/kg) cohorts.

In general, below rules apply to the derivations of efficacy endpoints related to hemoglobin and RBC transfusion data unless specified otherwise:

- Hemoglobin measurements within 7 days following RBC transfusion will be excluded from efficacy analysis
- For each patient, all efficacy endpoints will be derived based on the last dose + 56 days or the last date from transfusion record data, whichever is earlier.

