#### 10.2.1. Other Treatments for MDS

If treatment with azacitidine, decitabine, lenalidomide, ESA, or G-CSF is required during the ACE-536 treatment period, the patient should be discontinued from treatment with study drug and complete the end of treatment visit and enter the follow up period. Iron chelation therapy is allowed unless initiated within 56 days prior to C1D1.

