3.2. Treatment Discontinuation

Patients will be informed that they have the right to discontinue treatment and/or withdraw from the study at any time for any reason without prejudice to their medical care.

A patient may be discontinued from treatment for any of the following reasons:

- Patient's request
- Patient's unwillingness or inability to comply with the protocol
- Pregnancy
- Use of prohibited medication (e.g., ESA)
- Medical reason or adverse event, at the discretion of the investigator and/or the medical monitor
- Lack of effect (e.g., worsening anemia for NTD patients as evidenced by sustained reduction in Hgb by ≥ 2 g/dL over 8 weeks or transfusion dependence), to be discussed with the medical monitor
- Disease progression (as per IWG criteria¹ for altering natural history of MDS. See [Appendix 3](#)):

- For patients with 5-10% blasts, a second bone marrow sample should be collected within 4 weeks for clinical assessment (e.g., cytomorphology, cytogenetics) to confirm progression before discontinuing patients from treatment.
- Persistent increase in white blood cell (WBC) count as per Patient Dose Modifications (protocol Section 10.8)
- Presence of $\geq 1\%$ blasts in peripheral blood as per Patient Dose Modifications in protocol Section 10.8
- Hypersensitivity reaction to study drug
- At the discretion of the sponsor (e.g., termination of the study or a dose level)
-

A patient may be withdrawn from the study for any of the following reasons:

- Patient's request
- Patient's unwillingness or inability to comply with the protocol
- Death
- Lost to follow-up
- At the discretion of the sponsor (e.g., termination of the study)

The reasons for study withdrawal and/or treatment discontinuation must be recorded in the patient's CRF. The investigator must notify the sponsor, the medical monitor and the contract research organization (CRO) immediately when a patient has been discontinued/withdrawn due to an AE. Patients who discontinue treatment early should complete the end of treatment (EOT) follow-up visit at the time of discontinuation and then complete the post-treatment follow-up (PTFU) and end of study (EOS) follow-up visits approximately 28 and 56 days later, respectively.

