5.7.1. Primary Efficacy Endpoint

The primary efficacy endpoint is the modified erythroid response (mHI-E), defined as below:

- For low transfusion burden (LTB) patients, a hemoglobin increase of ≥ 1.5 g/dL from baseline for ≥ 14 days (in the absence of RBC transfusions). Hemoglobin measurements within 7 days following RBC transfusion will be excluded from analysis.
- For high transfusion burden (HTB) patients, a ≥ 4 units or $\geq 50\%$ reduction in RBC transfusion burden during any rolling 8-week window on treatment compared to baseline. The rolling 8-week window starts on Day 1 and increments by 1 day, e.g., from day 1 to day 56, day 2 to day 57, day 3 to day 58, etc.

A point estimate of the proportion of patients achieving a modified erythroid response will be presented along with its associated exact 95% confidence interval (CI) based on binomial distribution for LTB and HTB patients separately. The complete hemoglobin measurements and RBC transfusion records will be listed for each patient.

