5.7.2.4. Time to and Duration of HI-E Response

Time to and duration of HI-E response will be analyzed for HI-E responders only.

Time to HI-E response will be defined as the time from the first dose date to the first date of any rolling 8-week window achieving HI-E response.

Duration of HI-E response will be defined as below for LTB and HTB patients, respectively:

- a. For LTB patients, duration of HI-E response will be calculated as the longest interval during which all hemoglobin measurements having increase of ≥ 1.5 g/dL from baseline.
- b. For HTB patients, duration of HI-E response will be calculated as the time from the starting date of the first rolling 8-week window achieving response to the last date of the consecutive rolling 8-week window achieving response. When there are multiple disjoint intervals with response, the longest interval will be used.

Patients with response ongoing at the last record date will be censored. Both time to and duration of HI-E response will be analyzed as continuous variables and summarized by descriptive statistics. In addition, duration of HI-E response will also be analyzed as a time to event endpoint. The survival curves will be estimated using Kaplan-Meier method if the number of patients is more than 5.

The derivations of time to and duration of mHI-E (or HI-E) response will be listed for each patient.

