5.13. Protocol Violations or Deviations

Protocol violations and deviations will be reviewed and may result in a patient and/or patient visit data being excluded from the statistical summaries. All decisions regarding exclusion of any patient data will be made and recorded during the final data review.

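### SAP 5.7 does not stop efficacy data when an ESA or other MDS drug starts, so that drug's effect can count as an ACE-536 response, mainly in high-transfusion-burden patients

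*SAP*

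**What the plan says.** - **Data horizon.** SAP 5.7: "all efficacy endpoints will be derived based on the last dose + 56 days or the last date from transfusion record data", whichever is earlier. The rule applies unless specified otherwise.
- **Exclusions.** SAP 5.2: "All data in the database will be used in the analysis, with the exception of exclusions defined in section 5.7 for efficacy analyses". Apart from the horizon, 5.7 excludes only hemoglobin measured within 7 days after an RBC transfusion.
- **HTB response.** SAP 5.7.1 asks for a fall of at least 4 units or at least 50%, as a "reduction in RBC transfusion burden during any rolling 8-week window on treatment compared to baseline". HTB HI-E (SAP 5.7.2.2) uses the same kind of window with the 4-unit criterion. The SAP does not define *on treatment*.
- **Duration.** SAP 5.7.2.4: "Patients with response ongoing at the last record date will be censored". A new drug is not a censoring event.
- **What happens when another drug is needed.** SAP 3.2 lists ESA use among the reasons for stopping ACE-536 and adds: "Patients who discontinue treatment early should complete the end of treatment (EOT) follow-up visit at the time of discontinuation". Two later visits follow. Protocol 10.2.1 says that if azacitidine, decitabine, lenalidomide, an ESA or G-CSF is required during the treatment period, "the patient should be discontinued from treatment with study drug and complete the end of treatment visit and enter the follow up period".
- **Data review.** Under SAP 5.13, violations "may result in a patient and/or patient visit data being excluded from the statistical summaries", decided at the final data review. SAP 5.13.1 lists patients with unauthorized concomitant therapy.

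**The concern.** Read together, these sections keep a patient's hemoglobin and transfusion records in the efficacy derivation for up to 56 days after the last dose, even when another active drug starts in that time. The HTB endpoints need only one qualifying window, so extra days can add a response but can never remove one. The error in the response rate therefore runs upward only, and it comes from patients in whom ACE-536 failed and something else was tried.

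The trial has no control arm to offset this. HTB results are reported separately, and expansion cohort 1 plans a minimum of only 10 HTB patients, so a single misattributed response is visible in the result.

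**Working it through.** Notation: L is the study day of the last dose. A new drug starts on day L+s.

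**1. The plan's nearest figure (background only).** SAP 3.3 gives about 80% power for 25 patients, 10% against 30%, one-sided 0.05. An exact one-sample binomial rule of at least 6/25 has alpha 0.033 and power 0.807, which reproduces it. The concern does not depend on this figure.

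**2. Overlap with the last HTB window.** If windows run to the 5.7 cut-off, the last one is L+1 to L+56. Days on the new drug, counting the start day, are 57 − s:

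| Start | Days of 56 | Share |
|---|---|---|
| L+14 | 43 | 77% |
| L+21 | 36 | 64% |
| L+28 | 29 | 52% |

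**3. How many windows are touched.** Windows start on Day 1 and move by one day to the end at L+56, so there are L+1 of them. With a start at L+21, a window is touched if it ends on or after L+21.

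| Doses | L | Windows | Touched |
|---|---|---|---|
| 1 | 1 | 2 | 2 |
| 2 | 22 | 23 | 23 |
| 3 | 43 | 44 | 36 |
| 4 | 64 | 65 | 36 |
| 5 | 85 | 86 | 36 |

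After one or two doses no window is free of the new drug. Some touched windows overlap by a single day.

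**4. Can a response be created?** Assume ACE-536 has no effect, the new drug starts at L+14, and L is Day 64 or 85.
- *Baseline 4 units, given as 2 units every 28 days.* Every window holds 4 units. If the session due between L+29 and L+56 is avoided, the last window holds 2 units, a 50% fall, so mHI-E is met.
- *Baseline 8 units, given as 2 units every 14 days.* If sessions stop from the one due between L+29 and L+42, the last window holds 4 units. That is a fall of 4 units and 50%, so mHI-E and HI-E are both met.

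Both results hold for all 28 and all 14 possible session timings. If data end at L+13, the lowest window stays at 4 and 8 units, and neither patient responds.

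**5. How strong must the new drug be?** Take an even transfusion rate and an effect from the day after the start. For a baseline of 4 to 8 units, the required cut in rate is 28/(56 − s): 67% at s = 14, 80% at s = 21 and 100% at s = 28. For a baseline of 12 units, where 4 units is one third, it is (56/3)/(56 − s): 44%, 53% and 67%.

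With regular 2-unit sessions that cease more than 7 days after a start at L+21, and L on Day 22, 43 or 85, the share of timings counted as mHI-E is 100% for baselines of 4 or 8 units and 44–50% for 6 units. It is 0% without the new drug and 0% with a stop at its start.

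**6. Other endpoints.**
- *LTB mHI-E.* If a patient discontinues at L+21, EOT is at L+21 and the next visit at L+49; EOS at L+77 (±7) is past the horizon. One scheduled hemoglobin on the new drug cannot show 14 days. After a full course (L = Day 85), two such values require a start before EOT on Day 113. Exposure is low.
- *LTB HI-E.* An interval of at least 8 weeks ending by L+56 must begin by L, so the new drug alone cannot create it.
- *RBC-TI and durations.* RBC-TI needs more than 8 weeks, so its run must also begin by L. The new drug can complete or prolong a run that began on ACE-536.

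**7. Illustrative size.** Let q be the assumed share of non-responders who start such a drug. One third of these respond (the ESA figure for unselected patients in Protocol 7.1). Observed rate = 0.10 + 0.90 × q/3:
- q = 5%: 0.115
- q = 20%: 0.16

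With 10 HTB patients and 9 non-responders, the expected number of extra responders is 9 × 0.05/3 = 0.15 to 9 × 0.20/3 = 0.6. One extra responder turns 1/10 (exact 95% CI 0.3–44.5%) into 2/10 (2.5–55.6%).

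**The case against.** **The *on treatment* wording may already exclude these data.** The 5.7 rules are general and yield to anything more specific. SAP 5.5 counts exposure to last dose + 21 days, and the protocol's dropped Efficacy Evaluable definition takes transfusion data only to EOT. If windows end at L+21 or L+28, a drug started at L+14 covers at most 8 or 15 days (21 − 14 + 1; 28 − 14 + 1), and both worked examples disappear. This stands as a limit on size. It does not remove the problem: the SAP sets neither limit, 5.7 names all efficacy endpoints, and two programmers could reach different primary results.

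**Patients can be identified.** Unauthorized therapy, medications and transfusions are all listed. True, but a listing does not change the estimate. Exclusion under 5.13 is optional and is decided in an open-label trial with outcomes known. Protocol 10.2.1 addresses starts during the treatment period, so a start in follow-up may not count as a violation.

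**The event may be rare and the next drug weak.** Many HTB patients enter through cohorts that require erythropoietin above 500 U/L, or ESA failure, intolerance or unavailability, and all patients must lack a suitable alternative. One third is therefore an upper-end value for ESAs. This stands. Lenalidomide and the azanucleosides remain possible.

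**The examples are favorable.** They use regular sessions and a new drug that stops transfusions. This also stands: a later start needs an 80–100% cut at baselines of 4 to 8 units. If transfusions instead occur at random, many windows qualify by chance with no new drug, and the added share is smaller. For 8 units and L = Day 85, 72.5% qualify without it and 86.2% with an 80% cut from L+21.

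**Protocol version.** The SAP follows amendment 06, while the protocol supplied has no expansion cohort 3, so section 10.2.1 may have changed. SAP 3.2 alone supports the ESA case.

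**Conclusion.** The concern holds. The derivation rule can credit ACE-536 with the effect of the next drug, and no section truncates, censors or classes such a patient as a non-responder. The main exposure is HTB mHI-E and HTB HI-E, provided *on treatment* follows the 5.7 cut-off. It is low for LTB mHI-E and minimal for a new LTB HI-E response.

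The size cannot be fixed from the documents. The 11.5–16% range rests on an assumed 5–20% start rate and an upper-end one-third response. For 10 HTB patients the same inputs imply fewer than one extra responder on average, but a single case moves the rate by 10 points. No formal test is planned, so the damage is to the reported rates, confidence intervals and durations. The rule should be fixed before database lock.

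**What to change.** In SAP 5.7, end each patient's efficacy derivation at the earliest of:
1. last dose + 56 days;
2. the last date on which transfusion status was assessed (clarifying what the last transfusion-record date means);
3. the day before the first dose of an ESA, lenalidomide, azacitidine, decitabine or other MDS-directed drug (for HI-N, also G-CSF). Name the drugs in a list fixed before database lock.

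Count a patient with no qualifying response by that date as a non-responder, and censor an ongoing response there. Define *on treatment* in 5.7.1, 5.7.2.1, 5.7.2.2 and 5.7.2.3 to match. List the patients whose data are cut by item 3, so that readers can see whether any result depends on it.

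The cost is a few sentences and one derived date from concomitant-medication start dates already collected. No clinical rule changes. The response rate may fall slightly and some durations will be censored earlier. An HTB patient cut before Day 56 has no complete window and counts as a non-responder. If no patient is affected, no result changes because of item 3.

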Consistent with results from the nonclinical pharmacology studies, ACE-536 administration resulted in a mean maximum increase in hemoglobin (at any timepoint during the study) of 1.3 g/dL in the 0.25 mg/kg group. The maximum hemoglobin increase from baseline at any timepoint for patients in the 0.25 mg/kg group ranged from 0.6 to 2.0 g/dL. The mean hemoglobin increase from baseline in that treatment group was at least 0.6 g/dL from Day 8 through Day 57, compared with a mean hemoglobin decrease from baseline in the placebo group of up to 0.6 g/dL through Day 43 ([Figure 2](#)).

**Figure 2: Mean ( $\pm$ SD) Change from Baseline of Plasma Hemoglobin (g/dL) in Healthy Volunteers Treated with One or Two Doses of ACE-536**

The preliminary results from this phase 1 study suggest a positive effect of 0.25 mg/kg ACE-536 on increasing hemoglobin in healthy subjects. Doses up to 0.25 mg/kg were generally safe and well-tolerated.

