## 10. TREATMENT OF PATIENTS

### 10.1. Selection and Timing of Dose for Each Patient

Once a patient is enrolled, the appropriate dose of ACE-536 will be administered as a subcutaneous injection on Cycle 1 Day 1. Subsequent doses will be administered every 3 weeks on Day 1 of the cycle. Study day  $85 \pm 2$  days is the last possible study day that ACE-536 can be administered, regardless of the cycle. Dose reductions may be required for individual patients as outlined in the Patient Dose Modifications Rules ([Section 10.8.1](#)). If a dose delay is required, the patient will return weekly for assessment of hematology results and adverse events until the patient is eligible to receive the next dose of ACE-536. Patients will be asked to return to the clinic for three follow up visits, occurring approximately 28, 56, and 84 days after their last dose of ACE 536. If a patient has a positive anti-drug antibody (ADA) result at the last visit, the patient may be asked to return for additional ADA testing every three months, until a negative result is obtained or the result is considered to be stabilized.

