**Table 4: Patient Dose Modification Rules**

Observation on Dosing Day	Action	ACE-536 Dose Modification a
Hemoglobin $\geq$ 12 g/dL	Hold dose and monitor patient weekly until hemoglobin $<$ 11 g/dL	Resume dosing once hemoglobin $<$ 11 g/dL
Hemoglobin $\geq$ 2 g/dL increase from the previous dosing day (not attributable to RBC transfusion)	Continue dosing	Reduce the dose by 1 dose level a
Non-hematologic adverse event $\geq$ Grade 3, at least possibly related to study drug	Hold dose and monitor patient weekly until resolution of AE to $\leq$ Grade 1 or baseline	Resume dosing upon resolution of the AE to $\leq$ Grade 1 or baseline, and reduce the dose by 1 dose level a,b
White blood cell (WBC) count $\geq$ 13,000/ $\mu$ L c	
 
Dose delay until WBC <math><</math> 13,000/<math>\mu</math>L and resolution of associated condition (e.g., infection) within 6 weeks
 
Discontinue treatment if WBC <math>\geq</math> 13,000/<math>\mu</math>L persists for more than 6 weeks
 
Discontinue treatment if clinically significant cytomorphologic changes on bone marrow aspirate compared to baseline.
 
	

a Dose level refers to dose levels listed in [Table 3](#).

b Patients who require more than 2 dose reductions due to an AE should be discontinued from treatment and complete the EOT, PTFU and EOS visits.

c The investigator may contact the medical monitor and forward appropriate supporting documents for review and discussion prior to making decision regarding treatment discontinuation.

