5.7.2.2. HI-E Response Rate

Erythroid (HI-E) response will be defined following IWG 2006 criteria.

- For low transfusion burden (LTB) patients, a hemoglobin increase of ≥ 1.5 g/dL from baseline during any rolling 8-week in the absence of transfusion. The rolling 8-week starts and ends at a hemoglobin measurement date with duration $>= 8$ weeks.
- For high transfusion burden (HTB) patients, a reduction by ≥ 4 units of RBC transfusions during any rolling 8-week window on treatment compared to baseline.

A point estimate of the proportion of HI-E responders will be presented along with its associated exact 95% confidence interval based on binomial distribution for LTB and HTB patients separately. HI-E response will also be listed for each patient.

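### For low-burden patients whose high-hemoglobin hold is never released, the SAP's cut-off at last dose + 56 days can discard collected hemoglobin, cost an HI-E response and shorten its recorded duration

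*SAP*

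**What the plan says.** The cut-off is in SAP 5.7: "all efficacy endpoints will be derived based on the last dose + 56 days". The same sentence adds a second limit: "endpoints will be derived based on the last dose + 56 days or the last date from transfusion record data, whichever is earlier". It is introduced as a general rule for endpoints "related to hemoglobin and RBC transfusion data unless specified otherwise". The HI-E sections (SAP 5.7.2.2 and 5.7.2.4) state no exception.

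For LTB patients (fewer than 4 RBC units in the 8 weeks before dosing), HI-E is a rise of at least 1.5 g/dL. SAP 5.7.2.2 sets the window as follows: "The rolling 8-week starts and ends at a hemoglobin measurement date with duration" of at least 8 weeks. For high transfusion burden (HTB) patients it is a reduction of at least 4 "units of RBC transfusions during any rolling 8-week window on treatment compared to baseline". Duration (SAP 5.7.2.4) is the longest interval with all values at or above the threshold in LTB patients. It is summarized descriptively and by Kaplan-Meier, with ongoing responses censored at the last record date.

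Protocol Table 4 applies when hemoglobin is 12 g/dL or more on a dosing day: "Hold dose and monitor patient weekly until hemoglobin" is below 11 g/dL, after which dosing resumes. Protocol 10.1 adds that Day 85 ± 2 "is the last possible study day that ACE-536 can be administered, regardless of the cycle". The protocol synopsis (Criteria for Evaluation) plans erythroid response assessment for up to 24 weeks.

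**The concern.** The length of observation depends on the outcome. A strong rise triggers the hold, the hold fixes the last-dose date, and the SAP counts its 56 days from that date. Meanwhile the patient may still be in the treatment period with weekly hemoglobin checks. A weaker responder who keeps receiving doses is observed to Day 141.

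What is at stake is the secondary HI-E rate in LTB patients and the HI-E duration; both would be understated for some of the patients with the largest rises. SAP 5.7 reports efficacy by dose cohort and separately for LTB and HTB patients. Escalation cohorts have 3 to 6 patients, so one misclassified patient moves an LTB rate by at least 1/6, about 17 percentage points. In a group of 25 it moves the rate by 4 points.

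The cut-off also stops short of the protocol's 24-week assessment, and SAP 5.15 does not list it among the changes from the protocol.

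**Working it through.** **Inputs.** Dose days are 1, 22, 43, 64 and 85, and the first scheduled post-dose hemoglobin is Day 8 (schedule of events). The cut-off is L + 56, where L is the last-dose day (SAP 5.7). LTB HI-E needs a span of at least 56 days (SAP 5.7.2.2). Follow-up visits fall about 28, 56 and 84 days after the last dose (protocol 10.1). LTB entry requires mean hemoglobin below 10.0 g/dL (protocol 9.3.1).

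**The plan's own calendar.** With L = 85: 85 + 28 = 113, 85 + 56 = 141, 85 + 84 = 169. These match the EOT, PTFU and EOS days in SAP 5.1. For a fully dosed patient the cut-off is therefore Day 141, 28 days before EOS.

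**Holds that are never released.** If every value in the window must show the rise, then cut-off − onset ≥ 56, so onset ≤ (L + 56) − 56 = L. The longest span to the cut-off is (L + 56) − 8.

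| Last dose L | Hold starts | Cut-off | Days short of 141 | Longest span from Day 8 | Latest qualifying onset | EOS if L + 84 | Latest onset with data to L + 84 |
|---|---|---|---|---|---|---|---|
| 1 | 22 | 57 | 84 | 49 | none | 85 | 29 |
| 22 | 43 | 78 | 63 | 70 | 22 | 106 | 50 |
| 43 | 64 | 99 | 42 | 91 | 43 | 127 | 71 |
| 64 | 85 | 120 | 21 | 112 | 64 | 148 | 92 |
| 85 | none | 141 | 0 | 133 | 85 | 169 | 113 |

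For L = 1 a 56-day window would have to start on Day 1, before any drug effect, so no onset qualifies. The cut-offs on Days 57 and 78 fall before Day 85, inside the treatment period.

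**Case 1: one dose.** Take a baseline of 9.5 g/dL or less, a hold from Day 22, no transfusion, and hemoglobin of at least 11 at every check to Day 85. Each value is at least 11 − 9.5 = 1.5 g/dL above baseline, so the response lasts at least 85 − 22 = 63 days. The derivation sees 57 − 22 = 35 days, or at most 57 − 8 = 49, and scores a non-responder.

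**Case 2: two doses, held from Day 43.** Onset on Day 8, 15 or 22 gives 70, 63 or 56 days to Day 78 and qualifies. Onset on Day 29, 36 or 43 gives 49, 42 or 35 days and fails. If the response persists to L + 84 = Day 106, the spans are 77, 70 and 63 days. For onset on Day 29, the check on Day 85 alone would suffice (85 − 29 = 56).

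**What is not blocked.**
- Primary mHI-E needs 14 days; even with one dose, Day 8 to Day 57 gives 49.
- HTB HI-E windows start on Day 1, so 57 − 55 = 2 windows remain with one dose, against 141 − 55 = 86 with five.

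**Duration.** The longest measurable LTB duration at the cut-off is 49, 70, 91, 112 or 133 days for L = 1, 22, 43, 64 or 85. With data to L + 84 it is 77, 98, 119, 140 or 161. Every patient loses the last 28 scheduled days. Held patients also lose the difference from Day 141.

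**Visit windows.** EOT is 28 ± 7 days after the last dose and PTFU 28 ± 7 days after EOT, so PTFU falls 42 to 70 days after the last dose. A PTFU value later than day 56 is dropped for any patient, held or not.

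**The case against.** The strongest defense is that 56 days gives a uniform exposure window. The healthy-volunteer half-life in protocol 7.3 is 15.5 to 18.5 days, so 56 days is about 3.0 to 3.6 half-lives. A longer window for held patients alone would credit them with time off drug: up to Day 141 after one dose is 140 days, about 7.6 to 9 half-lives. That stands. It is why a uniform all-data analysis belongs beside any change.

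Several stronger readings are tempting, and the documents do not support them.

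- **All held patients lose follow-up.** A released hold leads to a later dose, and the cut-off moves with it. Below a baseline of 9.5 g/dL the response level lies under 11, so dosing can resume during a response (baseline 8.5, hemoglobin 10.5).
- **HI-E is generally impossible under a hold.** That is so only for one-dose LTB patients, and only if all values must show the rise. SAP 5.7.2.2 does not say so; the wording comes from the duration rule in 5.7.2.4.
- **All reported durations are cut short.** Kaplan-Meier censors ongoing responses. Direct shortening is confined to the descriptive summary. Censoring brought on by high hemoglobin may be informative, but that is a weaker point.
- **Every hold at C5D1 discards data from Days 121 to 141.** If follow-up is dated from a last dose on Day 64, nominal PTFU is Day 120 and EOS Day 148, with no nominal visit between.
- **Phase 1 shows that such responses persist.** Protocol 7.3 says "The mean hemoglobin increase from baseline in that treatment group was at least 0.6 g/dL from Day 8 through Day 57". That is a 0.6 g/dL mean rise in healthy women with mean hemoglobin 13.2 g/dL, not a 1.5 g/dL response in MDS.
- **Dose-response is flattened.** The frequency of holds by dose is not given.

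HI-E is secondary and descriptive, with no formal testing, and full hemoglobin records are listed. This limits the consequence but does not remove the misclassification.

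**Conclusion.** The point holds in a limited form. For LTB patients whose high-hemoglobin hold is not released by Day 85 ± 2, the cut-off falls 21 to 84 days before that of a fully dosed patient and can discard hemoglobin already collected. On the all-values reading, one-dose patients cannot be HI-E responders, and patients with two or more doses lose HI-E when onset follows the last dose. Descriptive durations are shortened. Primary mHI-E and HTB HI-E remain attainable.

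This rests on four assumptions:
- the all-values reading of LTB HI-E;
- weekly hemoglobin checks that continue through the hold;
- no earlier cut from the last transfusion-record date, which the SAP does not define for patients without transfusions;
- a hold rule that is the same in amendment 06, on which the SAP is based. The supplied protocol lacks expansion cohort 3 and is a different version.

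The documents do not give the number of patients affected, nor say how EOT and EOS are dated when a hold runs to Day 85. The size of the bias therefore cannot be stated. The change is worth making because it is cheap, not because the main result is in doubt.

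**What to change.** Amend the SAP before database lock:

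1. In 5.7, for patients not discontinued from treatment, set the cut-off for HI-E and its duration no earlier than Day 141, using whatever hemoglobin was collected. Say which reading of LTB HI-E applies, and define the on-treatment period and the last record date.
2. Add a sensitivity analysis of HI-E rate and duration in all patients, using all hemoglobin through EOS. This matches the protocol's 24-week assessment and treats held, discontinued and fully dosed patients alike. It is also what recovers the EOS value after a hold at C5D1, nominally Day 148, which a Day 141 limit would miss.
3. Flag responders whose qualifying window falls in a hold.
4. List the cut-off in 5.15 as a change from the protocol.

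Extending the cut-off only to the PTFU visit would add almost nothing, because PTFU is itself about 56 days after the last dose.

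The cost is a few sentences, a change to the derivation program and one extra table. No new data are needed and no dosing rule changes. The downside is that some off-drug time is counted, which the flag and the uniform sensitivity analysis make visible.
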